Specific aims: **1)** Determine if dyads in the TIP-C+SMSH as compared to the SMSH alone group created by the first randomization will have: a) lower depression, anxiety, and summed severity of 13 other symptoms at weeks 1-12, 13, and 17 (primary outcomes); b) lower use of healthcare services (hospitalizations, urgent care or emergency department [ED] visits) during 17 weeks (secondary outcomes); c) greater self-efficacy, social support, and lower caregiver burden during weeks 13 and 17 (potential mediators). **2)** Among nonresponders to the SMSH alone after 4 weeks, determine if dyads assigned to TIP-C+SMSH as compared to the SMSH alone group created by the second randomization will have better primary and secondary outcomes and potential mediators at weeks 5-12, 13, and 17. **3)** Test the interdependence in survivor's and caregiver's primary and secondary outcomes. **4)** Determine which characteristics of the dyad are associated with responses to the SMSH alone during weeks 1-4 and optimal outcomes for the dyad during weeks 1-12, 13 and 17 so as to determine tailoring variables for the decision rules of individualized sequencing of interventions. Findings will be used to improve symptom management and reduce distress in survivor-caregiver dyads.

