Randomization. Following the baseline interview, dyads will be randomized to either SMSH alone (N=172 post-attrition) or to TIP-C+SMSH (N=60 post-attrition). A minimization algorithm will be programmed by [name] to balance arms by recruitment location, site of cancer, stage of cancer (early versus late), type of treatment, and survivor's relationship to the caregiver (spouse vs non-spouse).²³⁹ The second randomization will occur for those who do not respond to the SMSH alone after the first 4 weeks using the same approach as the first randomization except in 1:1 ratio. The study coordinator will run the computer algorithm from the main study office (Tucson) to ensure allocation, concealment, and blinding.

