6.0 MEASURES/DATA COLLECTION INSTRUMENTS

Describe all forms, questionnaires, instruments or other specific methods used to collect data. Include complete copies of all forms, interview guides, survey questionnaires, in Appendix I.

Measures

Patient Reported Outcomes Measurement Information System (PROMIS)²⁴⁹ measures are suitable for both survivors and caregivers, have been developed using sophisticated measurement techniques, tested with over 21,000 individuals, calibrated to produce T-scores based on the general population, and are available in either English or Spanish. The available short forms have evidence of good reliability and validity.²⁴⁹ Our other measures also have good reliability ($\alpha > .80$)^{41,84,178,205} and validity, have been translated²⁴⁰ and tested with Spanish speaking participants in our pilot studies.³¹

Primary outcomes.

Caregivers' and survivors' symptoms will be measured using the adapted General Symptom Distress Scale (GSDS),^{124,250} a brief instrument that allows for a quick assessment of symptoms, which is especially important during weekly calls. It evaluates 15 symptoms: shortness of breath, nausea, vomiting, pain, sleep difficulties, bowel problems, numbness or tingling, skin rashes or sores, swelling in hands and feet, difficulty concentrating, poor appetite, cough, depression, anxiety, fatigue. Respondents indicate presence of each symptom (yes/no) and rate their severity on the scale from 1 to 10. The ability to manage symptoms is also assessed on a scale from 1=cannot manage to 10=can manage extremely well. The GSDS has good test-retest and internal consistency reliability and predictive and construct validity in both English and Spanish.²⁵⁰ The 0-10 ratings of depression and anxiety and the summed severity of other 13 symptoms will be derived at each weekly contact, baseline, 13, and 17 week interviews.

Survivors' symptom response on depression and/or anxiety during weeks 1-4 as a criterion for rerandomization.

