8.0 STATISTICAL CONSIDERATIONS

Analysis Plan for answering objectives including endpoint definitions, patient accrual objectives, and estimated duration of study. This section should be developed in consultation with appropriate biostatistician.

Potential Covariates and Future Tailoring Variables. These variables will be assessed during baseline interviews of survivors and caregivers. Demographic characteristics include caregivers' and survivors' age, education, work, ethnicity, race, acculturation, marital status, relationship between survivor and the caregiver, and living arrangement. Comorbidity will be measured with the Bayliss tool that queries the presence of 20 comorbidities,²⁵⁸ and we will also collect height and weight to calculate BMI. The validity and reliability of self-reported height and weight are adequate²⁵⁹⁻²⁶¹, and health risk estimates associated with BMI values are virtually the same, whether based on self-report or measured BMI values.²⁶² Caregiver's activities of survivor care will be measured using a checklist¹⁹, and quality of relationship will be measured using a 6-item index designed to assess the relationship quality. The index has established reliability with samples of married couples²⁶³ and has also been used to capture survivors' perceptions of the quality of relationship with their friend/family caregiver. Preferred language of intervention delivery will be tracked. Receipt and enactment of intervention strategies are measured during weeks 1-12. Receipt will be measured by the number of completed weekly sessions. Enactment of the SMSH strategies is assessed at the beginning of calls during weeks 2-12 as described in section C8c. Enactment of the TIP-C will be measured by tracking the implementation of behaviors discussed and completion of the assigned homework as documented in counselor's field notes for each session. Assessment of survivors' radiation, surgery, chemotherapy, targeted or hormonal therapy (dose, type, dates received), cancer site and stage, and medications (e.g., supportive agents for symptoms) will be collected from health record data corresponding with the time-on-study. Every effort has been made to keep respondent burden to a minimum and to distribute any burden over the course of the study. If needed, we can divide the assessments into two sessions over two days. Yet, few participants requested such accommodations in past studies.

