Exploratory Aim 4. The dyadic characteristics of responders will be compared to those of non-responders using t-tests, chi-square or Fisher's exact tests. Characteristics found to differ, along with mediators and other covariates listed in section C9d will be further considered as potential future tailoring variables. The decision rule (dd_1, dd_2) specifying the first and second intervention to achieve optimal outcome will be using the Qlearning optimization method^{258,270-272} implemented in SAS PROC QLEARN.^{273,274} The Q-learning algorithm proceeds backwards from the last decision to the first. Two Q-functions will be considered. The function $QQ_2(HH_2) = EE[YY_2|HH_2]$ is the expectation of the second stage outcome YY_2 given history after 2 stages, denoted by HH_2 : dyadic characteristics, outcomes observed during weeks 1-12, 13 and 17, and interventions received. The function $QQ_1(HH_1) = EE[YY_1 + \max QQ_2(HH_2)]$ uses history through the first intervention stage HH_1 . The conditional expectations in the Q-functions will be estimated from regression analyses for the primary outcomes, and the optimal decision rules will be found using backward induction by maximizing these functions.^{275,276} The product of this analysis will be identification of tailoring variables to operationalize the decision rules of selecting the optimal first intervention and switching from SMSH alone to TIP-C+SMSH. These personalized decision rules can then undergo testing in a future confirmatory RCT.

Potential Difficulties/Limitations and Alternative Approaches

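### Aim 4: the stage-2 Q-learning history includes outcomes from after the week-4 decision, so the stage-2 effect and its tailoring interactions are biased as written

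*Combined protocol and SAP*

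**What the plan says.** The Exploratory Aim 4 text in section 8.0, repeated in section 5.0, sets up two Q-functions. The second is the expectation of a second-stage outcome Y2 given H2. H2 is described as the history after both stages and comprises "dyadic characteristics, outcomes observed during weeks 1-12, 13 and 17, and interventions received". The first Q-function "uses history through the first intervention stage". Both expectations are to be estimated by regression for the primary outcomes, and the rule is found by maximising them.

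On timing, section 4.0 (Randomization) states: "The second randomization will occur for those who do not respond to the SMSH alone after the first 4 weeks". Section 6.0 says the symptom scores "will be derived at each weekly contact, baseline, 13, and 17 week interviews". H2 therefore lists every occasion after the second decision on which the primary outcomes exist.

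On tailoring variables, Aim 4 says: "Characteristics found to differ, along with mediators and other covariates listed in section C9d will be further considered as potential future tailoring variables". The covariate section says of its list: "These variables will be assessed during baseline interviews of survivors and caregivers". It then adds: "Receipt and enactment of intervention strategies are measured during weeks 1-12". Section 2.0 compares the mediators at weeks 13 and 17.

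**The concern.** A stage-2 Q-function should predict the later outcome from what is known when the second decision is made, plus the option chosen. Regressing on outcomes that follow the choice adjusts away part of its effect, or distorts it. The same plan handles this correctly in Aim 2: weeks 5-12, 13 and 17 are outcomes, and the model adjusts for week-4 severity, time and covariates.

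Three further problems follow.

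- **Usability.** A rule that needs values from after week 4 cannot be computed at week 4. Most candidate tailoring variables are baseline measures, so a rule using only those could be computed, but from biased coefficients.
- **Stage 1.** If the first stage runs to week 4, H1 contains data from after the first assignment, so the same fault arises one decision earlier. A biased maximum of Q2 also carries into the stage-1 regression.
- **Definition of the target.** Y1 and Y2 have no weeks. The functions are maximised, although lower symptom scores are better.

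The stated product of Aim 4 is the set of tailoring variables and the rule for switching from SMSH alone to TIP-C+SMSH, for possible testing in a confirmatory trial. Both rest on the stage-2 effect and its interactions.

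**Working it through.** **The plan's own figures.** The documents give no effect, power or sample size for Aim 4. The design chain in section 4.0 does reproduce: 120/0.70 = 171.4, rounded up to 172; 172 + 60 = 232; 232/0.78 = 297.4, rounded up to 298. This fixes the stage-2 sample at 120 (60 per group).

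**Case 1: Y2 is in H2.** If Y2 is one of the listed outcomes, it is a regressor for itself. Then E[Y2 | H2] = Y2, and the coefficients of the assignment A2 and of its interactions are exactly 0. In simulation the largest absolute value was below 2e-14.

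**Case 2: Y2 is left out, but the other later outcomes stay.**

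Inputs and assumptions:
- Y2 is the week-17 value (assumed).
- There are 5 pre-decision values: baseline and weeks 1-4 (assumed).
- There are 9 post-decision values: weeks 5-12 and 13 (from the H2 definition).
- Within-arm correlation r is equal for all pairs, from 0.36 to 0.77. The range is in section 4.0; equality is assumed.

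With 14 equally correlated regressors, each has coefficient r/(1 + 13r). Hence

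coefficient of A2 = (effect at week 17) − [r/(1 + 13r)] × (sum of effects at weeks 5-13).

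The denominator is 1 + 13(0.36) = 5.68 or 1 + 13(0.77) = 11.01.

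| Pattern of the true effect | Formula | r = 0.36 | r = 0.77 |
|---|---|---|---|
| (a) Constant from week 5: share lost | 9r/(1+13r) | 3.24/5.68 = 0.570 | 6.93/11.01 = 0.629 |
| (b) Linear build-up, 1/8 at week 5 to 1 at week 12, then 1: share lost | 5.5r/(1+13r) | 1.98/5.68 = 0.349 | 4.235/11.01 = 0.385 |
| (c) Main effect constant, interaction building: crossover point relative to truth | (1−a)/(1−b) | 0.430/0.651 = 0.66 | 0.371/0.615 = 0.60 |
| (d) Week-17 effect half of the weeks 5-13 effect: coefficient as a fraction of the weeks 5-13 effect | 0.5 − a | −0.070 | −0.129 |

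In (a) and (b) the main effect and the interaction shrink by the same factor. The crossover point stays put and the loss is in detectability. In (c) the rule itself changes. In (d) the sign reverses once the week-17 effect is below 57%-63% of the weeks 5-13 effect.

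**Simulation** (4000 replicates, n = 120, illustrative main effect −0.39 and interaction −0.30; Monte Carlo SE at most 0.003). With the history stopped at week 4, the estimates are about −0.39 and −0.30. Adding weeks 5-13 gives, as main effect / interaction:

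| Pattern | r = 0.36 | r = 0.77 |
|---|---|---|
| Constant | −0.170 / −0.128 | −0.146 / −0.113 |
| Build-up | −0.256 / −0.196 | −0.242 / −0.187 |
| Fade to 50% (truth −0.195 / −0.15) | +0.027 / +0.023 | +0.050 / +0.038 |

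For the constant effect and a continuous tailoring variable with SD 1, power for the interaction at the 5% level falls from 0.45 to 0.11 (r = 0.36) and from 0.84 to 0.17 (r = 0.77).

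**Sensitivity to the pre-decision values included.** With weeks 1-4 only, the constant-effect loss is 9r/(1+12r): 3.24/5.32 = 0.61 and 6.93/10.24 = 0.68. With week 4 only, it is 9r/(1+9r): 3.24/4.24 = 0.76 and 6.93/7.93 = 0.87. A separate simulation of the week-4-only version agreed: a true −0.39 became −0.09 and −0.05.

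**The case against.** The strongest reply is that this is a slip of wording. Read literally, the stage-2 analysis is empty, and no analyst would report it. The same paragraph describes backward induction towards a switching rule, which needs pre-decision inputs. The listed weeks match the outcome window in the section 2.0 statement of Aim 4, so outcomes and history may simply have been run together. That is plausible, but nothing in the documents limits H2, and a plan has to be judged on the model it specifies.

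Some narrower points do stand:

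- **Mediators.** Their timing as tailoring candidates is unspecified, not necessarily late. Section 6.0 has the self-efficacy and social-support forms given in interviews, so baseline values should exist. Symptom-management self-efficacy comes from the weekly symptom scale. Receipt and enactment over weeks 1-12 do, however, include values from after the decision.
- **Size.** The loss for a constant effect runs from 57% to 87% depending on which pre-decision values enter, and another choice of Y2 would give other numbers.
- **Power.** The loss depends on the scale of the tailoring variable. For a balanced binary variable with the same −0.30 interaction, power goes from 0.16 to 0.08 and from 0.33 to 0.09, so it was low to begin with.
- **Reach.** Aim 4 is exploratory and has no power target.

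These points qualify the illustrations and the consequence. They do not rescue the definition of H2.

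**Conclusion.** The concern holds. As written, the stage-2 model gives either a null effect (Y2 inside H2) or a biased one (Y2 removed, later outcomes kept). That is an error in the specified model, not just missing detail.

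The zero in the first case is exact and needs no assumption. The sizes in the second case are illustrations, because the documents fix neither magnitude nor direction. Depending on how the effect evolves, true tailoring variables become harder to detect, the crossover point moves, or the sign reverses. The false-discovery adjustment planned for exploratory analyses does not correct a biased coefficient.

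The matter should be corrected, but it does not threaten the trial's main comparisons: Aims 1-3 are unaffected.

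**What to change.** Edit the Aim 4 text in both sections 5.0 and 8.0 before analysis:

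1. Limit H1 to baseline information.
2. Limit H2 to baseline data, first assignment, outcomes and receipt/enactment through week 4, and response status.
3. Write Q2 = E[Y2 | H2, A2] and fit it in the re-randomised non-responders, with A2-by-H2 interactions. For dyads with no second decision (responders and the initial TIP-C+SMSH arm), use the observed Y2 in the stage-1 step.
4. Define Y1 and Y2 by outcome and week, so that Y2 uses only outcomes from after the second decision and none of these is in H2. State whether the outcome is to be minimised or maximised.
5. Restrict every candidate tailoring variable, including mediators and receipt/enactment, to values measured before the decision it informs.

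The cost is a text change plus a sponsor decision on which outcomes and weeks form Y1 and Y2. The data through week 4 are already being collected.

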9.0 STUDY TIMELINE

List of all parameters and required intervals for observations, measurement of outcomes, intervention and intervals at which it is given.

Table 3 represents the timeline of the project over the 4 years. Table 4 represents the specific schedule of events for the project.

| Table 3: Timeline of the Project | Year 1 | | | | Year 2 | | | | Year 3 | | | | Year 4 | | | | |
|--|-----------|---|---|---|--------|---|---|---|--------|---|---|---|--------|---|---|---|---|
| | Quarters: | 1 | 2 | 3 | 4 | 1 | 2 | 3 | 4 | 1 | 2 | 3 | 4 | 1 | 2 | 3 | 4 |
| IRB approval, update manuals, hire/train staff | X | X | | | | | | | | | | | | | | | |
| Enroll subjects; deliver intervention; collect | | | X | X | X | X | X | X | X | X | X | X | X | X | X | X | |
| Complete survivor health record audits | | | X | X | X | X | X | X | X | X | X | X | X | X | X | X | |
| Set up/conduct analyses; annual/final reports | X | X | | X | | X | X | | | X | X | X | X | X | X | X | X |

Table 4 IRB #: 1804501501

PI: [name]

Schedule Of Events: Improving Informal Caregivers' and Cancer Survivors' Psychological Dis

| Study Item, Service, or Activity NOTES: | Timepoint NOTES: | Screening | Baseline (wk 0) | Weeks 2-4 | Weeks 2-12 | Follow-up (wk 13) | Follow-up (wk 17) |
|--|------------------|-----------|-----------------|-----------|------------|-------------------|-------------------|
| Study Item, Service, or Activity | | | | | | | |
| Inclusion / Exclusion Criteria | | X | | | | | |
| Consent and PHI Auth Signed | | X | | | | | |
| Enroll participant, enter into the queue for baseline via telephone | | | X | | | | |
| Telephone participant to do the baseline or reschedule based on their preference | | | X | | | | |
| Randomize participant post baseline into SMSH or SMSH+ TIP-C Intervention | | | X | | | | |
| Mail study welcome letter, Symptom Management Handbook | | | X | | | | |
| Intervention delivery via telephone | | | | X | | | |
| Rerandomized if survivor is not responding (SMSH only) | | | | X | | | |
| Intervention delivery via telephone (those initially randomized to TIP-C stop TIP-C at week 8; continue with SMSH) | | | | | X | | |
| Follow-up assessment via telephone | | | | | | X | X |
| Follow-up assessment via telephone | | | | | | | |
| Satisfaction and Debriefing via telephone | | | | | | | X |
| Participant is mailed a thank you letter and gift card to thank them for their time | | | X | | | | X |

10.0 DATA SAFETY AND MONITORING PLAN

Describe plans to monitor adherence to study protocol, integrity of data collection and intervention delivery. Include any plans regarding project quality assurance.

Data Safety and Monitoring Plan. This behavioral intervention study meets the definition of a clinical trial. Data and Safety Monitoring will be accomplished through multiple approaches:

Institutional Review Board (IRB) - All procedures related to data collection and safety will be approved by the University of Arizona (UA) Health Sciences Center IRB and by the independent Arizona Cancer Center Office of Clinical Trials. Processes will be established to guide collection, transfer and storage of data and training of staff to ensure data safety. Quality assurance (QA) reviews of data and staff will be performed as described below.

1. Security Procedures for Collection, Transfer and Storage of Electronic Data. Electronic files will consist of enrollment data, survey data at two time points, symptom data collected during the weekly calls, interventionist call data for survivors allocated to TIP-C + SMSH and survivor's medical record data (collected at enrollment and during medical record audit after survivors complete their 13 week interviews). First, enrollment data with identifiers will be stored separately from the study data. Second, all computers that will store data at the central location will be password protected. The system will have a secure login along with audit control mechanisms to meet the HIPAA guidelines. Third, servers will utilize state-of-the art security processes. Electronic copies of forms, such as the consent or HIPAA authorization form will be stored on a secure dedicated server with appropriate firewalls. The system will use encryption (SSL certificate) to transfer data between the machines. This technology is the same as that used for online e-commerce applications to protect consumer information. Servers are scanned for viruses and systems are in-place to detect attempts at unauthorized entry. All transactions to the database are stored in archive logs as re-do data and are accessible to enable quick recovery of all data should the need arise. Backup files are written nightly to back up servers.

2. Security Procedures for Collection, Transfer and Storage of Paper Data. Paper files will consist of consent and authorization forms and medical record audits. Paper copies of all forms will be faxed to the central study office for data entry. Faxed copies of medical records will be retained in locked storage cabinets at UA accessible only to study personnel.

3. Training of Staff.

Recruiters- will follow UA institutional processes for enrollment of patients to clinical trial(s). Training by the study Coordinator will occur in order to ensure recruiters understand eligibility criteria, study design and goals. Training will emphasize strategies to maximize enrollment and retention of minority participants. Additionally, training will occur to assure recruiters understand the function and importance of data gathered during the medical record audit at enrollment. Training will include completion of simulated cases. Booster training sessions will be scheduled as needed.

Interviewers/Data Collectors - will be carefully instructed and trained in appropriate interviewing techniques and will receive regular monitoring by the study Coordinator to ensure the ethics of research and scientific integrity and protection of confidentiality. Participants are asked prior to each interview if they want to continue and are given a toll-free number to contact UA if they have questions or concerns.

Interventionists- TIP-C interventionists will receive 24 hours of education, augmented by additional books and articles, about cancer diagnosis and treatment, psychological distress, and interpersonal counseling techniques with training protocols developed in previous studies (Appendix C). The interventionists will listen to 8-10 hours of counseling sessions recorded for training purposes. [name] will conduct interventionist training that will continue until the interventionists are rated as achieving > 90% on protocol implementation. Annual re-training will occur throughout the study.

Medical Record Auditors – will be the recruiters or are employees of each recruitment site with oncology experience but trained by the study Coordinator on collection of data for this study. Training will target job descriptions, and roles and responsibilities of group members and will consist of 1) an overview of project objectives, theoretical framework, and research design and rationale, 2) background and training on collecting data free from bias, 3) information on scale and item response issues; 4) protection of human patients and confidentiality issues; and 5) data and intervention monitoring and quality assurance procedures. Activities for training will consist of lectures, discussion,

4. Monthly Meetings – Monthly meetings with all research staff will be conducted to review accrual, attrition, discuss problems and/or concerns and ensure everyone understands and is following the protocol.

5. Quality Assurance Activities for Project Staff – Quarterly quality assurance (QA) will involve engaging in good data management activities. Procedures that include checking the integrity of data storage and examining frequency distributions to look for anomalies such as an excessive number of “don’t know” responses or problems with skip patterns will be in place.

Recruiters – Enrollment data will be monitored monthly for completeness and consistency. If any missing data are identified, the completion of missing fields will be requested and questions clarified during quarterly QA review of the data.

Interviewers - The level of quality of each interviewer and the interview process are monitored monthly by the study Coordinator and Investigators. A cadre of well-trained interviewers at UA is available and used by this team in previous studies. Early in the study, until proficiency is reached, the interviewers digitally record every interview for QA. Following initial training, interviewers will be required to record and submit 1 interview each month for review. There is no identifying information recorded. Booster training sessions are held with interviewers on a scheduled basis. Written feedback on the quality of the telephone interview is provided to all interviewers following review of each recording.

Interventionists - All sessions are digitally recorded and about 10% randomly reviewed throughout the study to maintain quality, with written and verbal feedback given to the counselors. [name] will supervise the intervention quality control activities. Through weekly case supervision, we will maintain fidelity of the intervention and counselor adherence to protocols. We will evaluate adherence (number required elements discussed/ total number of elements). [name] will listen to all sessions in English from the first 5 dyads (40 hours of supervision) and then randomly review 10% of sessions throughout the study. A bilingual counselor will review sessions in Spanish using established protocols as in past studies. Counselors who do not maintain 90% adherence will not be given new cases until retraining has occurred, and [name] will assume responsibility for those existing cases. Following retraining, 5 dyads will be monitored to ensure that >90% adherence is achieved and then we will return to randomly selected monitoring for quality control. Anyone unable to adhere to the standardized protocols is replaced after a second retraining.

Data - Quality assurance reports will be prepared on a quarterly basis by the statistical research assistant supervised by [name] and reviewed by the study Coordinator and investigative team. That is, for the internal audit, someone independent of the data collector will check the data. Data from 10% of the recorded interviews and intervention sessions compared to database entries. The acceptable error rate is 0.3 %, i.e., 3 out of 1,000 fields. All errors are corrected during the QA check. [name] will oversee preparation of the data report distributed to all investigators at least 5 days before the scheduled meeting. The report will include the summary of cumulative and quarterly accrual, randomization, cumulative attrition, and attrition by study group, gender, and race/ethnicity, adverse events and serious adverse events, data completeness and quality, and study Consolidated Standards of Reporting Trials (CONSORT) chart. Reports will also inform the Investigators about missing, invalid, or inconsistent data on selected key variables. For the external oversight, [name] who is not involved in the study has agreed to participate in QA meetings.

6. Identification of Adverse Effects- The following will be considered serious adverse events (SAE): death, attempted suicide, major depression, breach of confidentiality. Death, attempted suicide and major depression would not occur as a direct result of study interventions, however, could be encountered during implementation of this study due to the inclusion criteria of cancer survivors. A breach in confidentiality may result from participation in this study. The investigators have successfully trained staff to monitor and protect confidentiality of participants in large research studies conducted over the past two decades. Similar training strategies will be incorporated for training of staff in this study. Additionally, all research staff will complete the human subjects and HIPAA certification training.

The following will be considered adverse events (AE): severe symptoms requiring hospitalization or urgent care. Again, severe symptoms are not expected to result from participation in this study but may result from cancer, its treatment or other existing comorbid conditions.

Averse events and serious adverse events may be identified during implementation of the experimental protocols and are monitored by the Investigators in several ways.

Interviewers: Interviewers may identify both serious adverse events and/or adverse events

during completion of telephone interviews or telephone calls to schedule telephone interviews. **Interventionists:** The interventionists may identify both serious adverse events and/or adverse events during their telephone contacts with the participants.

